# 3 Study Design and Methodology

# 3.1 Overall Study design

This is a multicenter, randomized, double-blind, placebo-controlled clinical trial to evaluate the efficacy and safety of apatinib in the treatment of locally advanced/metastatic radioiodine refractory differentiated thyroid cancer (RAIR-DTC).

The eligible subjects will be randomly assigned to either the treatment group or control group in a 1:1 ratio. Apatinib or placebo will be given 500 mg orally once daily for 28 days. Apatinib treatment will be discontinued at the time of disease progression, intolerable toxicity, withdrawal of consent, or due to investigator's evaluation. Tumor imaging with CT or magnetic resonance imaging (MRI) will be done at the end of first and second treatment cycles, then every two treatment cycles thereafter. The efficacy will be assessed per RECIST version 1.1 by investigators. Safety assessment including vital signs, physical examination, blood and urine analysis, liver, kidney and thyroid function tests, electrolyte profile, electrocardiogram and ECOG performance status will be done every two weeks for one-two cycles, and at the end of each subsequent cycle. Adverse events will be graded according to the National Cancer Institute Common Terminology Criteria for Adverse Events (version 4.0). Survival status will be followed up every two months until death or loss to follow-up.

In the extension phase, subjects in the Apatinib group will continue the treatment when anticipated to benefit from apatinib treatment. For the subjects in the control group, they will be allowed to receive apatinib upon experiencing radiographic disease progression (PD) per RECSIT v1.1 by investigator. Extended treatments are terminated after progression disease, intolerable toxicity, and withdrawal of informed consents during extension phase.

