Note: (1) &: once every 2 cycles (the last day); (2) #: once every cycle (last day) and once every 2 cycles (last day) after 6 cycles of medication; (3) @: when the progressive disease or withdraw from the study in advance, if there is no such examination result within 4 weeks before the end of the trial, it needs to be collected within 7 days after the end of the study; (4) a: The subjects can increase the frequency of self-examination of vital signs according to their own conditions and fill in the relevant abnormal conditions in the research diary card. b: blood pressure monitoring: blood pressure monitoring is completed by the subjects themselves, at least three days a week in the first two cycles after medication, and once a week in the later cycles. Once abnormal, the blood pressure should be monitored to the normal level every day and recorded in the patient's diary card; in addition, the blood pressure is measured again by the researcher at each follow-up. During the blood pressure measurement, smoking and coffee drinking are prohibited within 30 minutes before the measurement, and at least 10 minutes of quiet rest are taken. During the measurement, the sitting position is taken, the elbow is placed at the same level as the heart, and each blood pressure measurement is taken on the same side. c. Myocardial enzyme spectrum and color Doppler ultrasound: supplement this examination when ECG is abnormal and has clinical significance; d: if chest, abdomen or pelvis imaging examination is negative at screening, X-ray or B-ultrasound should be used for examination during the study period; if X-ray or B-ultrasound shows positive results, CT or MRI scan should be used to confirm; e: the examination items include FT3, FT4, TSH, RT3 [RT3 can be selected as needed]; f: collect within 3 days after the first medication. (5) Tumor samples (tissue and blood) are collected when subjects include in this study. If a tumor sample is not collected, the reason should be record. (6) During the first two cycles of treatment, all examinations and life quality scores are performed within  $\pm 3$  days of the corresponding date, and after two cycles, all examinations and life quality scores are performed within  $\pm 7$  days of the corresponding date.

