# 7.2 Visit during the screening

The screening visit should be carried out within 14 days before the start of the trial. Informed consent should be signed, imaging examination (X-ray/CT/MRI/B ultrasound), ECG examination should be carried out. In case of precordial pain, palpitation and other symptoms, myocardial enzyme spectrum should be monitored (creatine kinase, lactate dehydrogenase, aspartate aminotransferase, creatine kinase isoenzyme,  $\alpha$ -hydroxybutyrate dehydrogenase) and color Doppler ultrasound should be performed (if necessary). Medical history should be collected within 7 days before the start of the trial, including previous treatment history, vital signs, physical examination and ECOG PS score, blood pressure test, blood routine (hemoglobin (HB), red blood cell (RBC), white blood cell (WBC), absolute neutrophil (ANC), neutrophil ratio (N), lymphocyte ratio (Lym), monocyte ratio (Mon), platelet count (PLT)), urine routine (urine protein, urine red blood cell (microscopic examination), urine white blood cell (microscopic examination)), stool routine, liver and kidney function (total bilirubin (TBIL), direct bilirubin (DBIL), indirect bilirubin (IBIL), ALT, AST, AKP, TP, ALB, BUN, Cr, UA, γ-GT, LDH), electrolytes (K, Na, Cl, CA), phosphorus (P)), coagulation function (PT, APTT (thrombin time), TT, fibrinogen (FBG), international standardized ratio (INR)), serum Tg and TgAb, thyroid function (FT3, FT4, TSH, RT3 [RT3 can be selected as needed]), life quality score, Hamilton Depression Scale score and (serum) pregnancy test (if there are clinical indications indicating pregnancy is possible) etc. Tumor samples (tissue and blood) are collected when subjects include in this study. If a tumor sample is not collected, the reason should be record.

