#### 3) At the end of the third week after the start of administration and after

Vital signs, physical examination (including skin toxicity, nausea, fatigue, tooth function such as looseness, tooth drop, etc.), ECOG PS score, life quality score, blood routine, urine routine, stool routine, liver and kidney function test, electrolyte test, blood coagulation function test and electrocardiogram examination are performed weekly, in case of precordial pain, palpitation and other symptoms, the myocardial enzyme spectrum should be detected immediately, and cardiac color Doppler ultrasound should be performed (subjects can increase the frequency of selfexamination of vital signs according to their own situation and fill in the relevant abnormal conditions in the research diary. The above examination is changed to once every 2 cycles after 6 cycles of medication.

The efficacy of tumor is evaluated every 2 cycles (imaging examination: CT/MRI/B ultrasound), serum Tg and TgAb levels are detected, and thyroid function is examined.

Blood pressure monitoring: the subjects should self-monitor the blood pressure at least once a week, once abnormal, they need to monitor to the normal level every day, and record in the patient's diary card. During the visit, the researcher measures the blood pressure, and the measurement method is the same as that in the first cycle.

4) The concomitant medication and AE should be observed and recorded at any time from the beginning of administration to 30 days after the end of administration.

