# 8 Efficacy evaluation and analysis

The efficacy assessment will be conducted at the end of the first and second cycles, as well as every eight weeks after that. The assessment will take place within 3 days after the completion of each period. From the third cycle, CT or MRI examinations will be performed within 7 days after completing of every two cycles.

Subjects who develop progressive disease during randomization phase will be unblinded and treat with apatinib until disease progression or at the discretion of the investigators.

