#### 3.2.2 Method of assessment

The same method of assessment and the same technique should be used to characterise each identified and reported lesion at baseline and during follow-up. Imaging based evaluation should always be done rather than clinical examination unless the lesion(s) being followed cannot be imaged but are assessable by clinical exam.

Clinical lesions: Clinical lesions will only be considered measurable when they are superficial and P10mm diameter as assessed using calipers (e.g. skin nodules). For the case of skin lesions, documentation by colour photography including a ruler to estimate the size of the lesion is suggested. As noted above, when lesions can be evaluated by both clinical exam and imaging, imaging evaluation should be undertaken since it is more objective and may also be reviewed at the end of the study.

Chest X-ray: Chest CT is preferred over chest X-ray, particularly when progression is an important endpoint, since CT is more sensitive than X-ray, particularly in identifying new lesions. However, lesions on chest X-ray may be considered measurable if they are clearly defined and surrounded by aerated lung. See Appendix II for more details.

CT, MRI: CT is the best currently available and reproducible method to measure lesions selected for response assessment.

This guideline has defined measurability of lesions on CT scan based on the assumption that CT slice thickness is 5mm or less. As is described in Appendix II, when CT scans have slice thickness greater than 5 mm, the minimum size for a measurable lesion should be twice the slice thickness. MRI is also acceptable in certain situations (e.g., for body scans). More details concerning the use of both CT and MRI for assessment of objective tumour response evaluation are provided in Appendix II.

Ultrasound: Ultrasound is not useful in assessment of lesion size and should not be used as a method of measurement. Ultrasound examinations cannot be reproduced in their entirety for independent review at a later date and, because they are operator dependent, it cannot be guaranteed that the same technique and measurements will be taken from one assessment to the next (described in greater detail in Appendix II). If new lesions are identified by ultrasound in the course of the study, confirmation by CT or MRI is advised. If there is concern about radiation exposure at CT, MRI may be used instead of CT in selected instances.

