#### 4.3.5 New lesions

The appearance of new malignant lesions denotes disease progression; therefore, some comments on detection of new lesions are important. There are no specific criteria for the identification of new radiographic lesions; however, the finding of a new lesion should be unequivocal: i.e., not attributable to differences in scanning technique, change in imaging modality or findings thought to represent something other than tumour (for example, some 'new' bone lesions may be simply healing or flare of pre-existing lesions). This is particularly important when the patient's baseline lesions show partial or complete response. For example, necrosis of a liver lesion may be reported on a CT scan report as a 'new' cystic lesion, which it is not.

A lesion identified on a follow-up study in an anatomical location that was not scanned at baseline is considered a new lesion and will indicate disease progression. An example of this is the patient who has visceral disease at baseline and while on study has a CT or MRI brain ordered which reveals metastases. The patient's brain metastases are considered to be evidence of PD even if he/she did not have brain imaging at baseline.

If a new lesion is equivocal, for example because of its small size, continued therapy and follow-up evaluation will clarify if it represents truly new disease. If repeat scans confirm there is definitely a new lesion, then progression should be declared using the date of the initial scan.

While FDG-PET response assessments need additional study, it is sometimes reasonable to incorporate the use of FDG-PET scanning to complement CT scanning in assessment of progression (particularly possible 'new' disease). New lesions on the basis of FDG-PET imaging can be identified according to the following algorithm:

• Negative FDG-PET at baseline, with a positive FDG-PET at follow-up is a sign of PD based on a new lesion

- No FDG-PET at baseline and a positive FDG-PET at follow up: If the positive FDG-PET at follow-up corresponds to a new site of disease confirmed by CT, this is PD. If the positive FDG-PET at follow-up is not confirmed as a new site of disease on CT, additional follow-up CT scans are needed to determine if there is truly progression occurring at that site (if so, the date of PD will be the date of the initial abnormal FDG-PET scan).

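### Sections 7.1 to 7.4 admit B-ultrasound, and in places X-ray, as tumour imaging, against the CT or MRI named in sections 3.1 and 8 and against the attached RECIST text

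*Protocol*

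**What the plan says.** Section 2.1 makes PFS by RECIST 1.1 the primary endpoint, and 3.1 has investigators assess it. On modality the protocol says the following.

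- Section 3.1: "Tumor imaging with CT or magnetic resonance imaging (MRI) will be done at the end of first and second treatment cycles", and every two cycles after that.
- Section 8: "From the third cycle, CT or MRI examinations will be performed within 7 days after completing of every two cycles".
- Section 7.1, imaging row: X-ray, CT, MRI and B-ultrasound are listed together.
- Section 7.2, screening: "imaging examination (X-ray/CT/MRI/B ultrasound", with no rule for choosing among the four.
- Section 7.3, item 3: "The efficacy of tumor is evaluated every 2 cycles (imaging examination: CT/MRI/B ultrasound". Section 7.4 gives the same list for the extension phase.
- Section 7.1, note d: "if chest, abdomen or pelvis imaging examination is negative at screening, X-ray or B-ultrasound should be used for examination during the study period". The note goes on: "if X-ray or B-ultrasound shows positive results, CT or MRI scan should be used to confirm".
- Attachment 1, section 3.2.2: "Ultrasound is not useful in assessment of lesion size and should not be used as a method of measurement". The same section asks for one method and technique per lesion from baseline through follow-up, and prefers chest CT to chest X-ray where progression is an important endpoint.

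**The concern.** Modality decides what can be measured and what can be seen, so it is part of the definition of a RECIST progression. Here the design section and the operational sections give different lists, and the operational sections are the ones a site works from at each visit. A site that follows 7.3 literally could assess efficacy by ultrasound and record a result that the attached RECIST text does not recognise as a measurement.

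Two errors in the primary endpoint could follow. A new lesion counts as progression, so a less sensitive test in a region thought clear can date the event late or miss it. Conversely, if the baseline was X-ray or ultrasound and CT is done later, an old small lesion can appear to be new. A false call has consequences: progression declared by the investigator permits unblinding and lets control subjects start apatinib (3.1, 7.4, 8).

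**Working it through.** **1. The passages side by side**

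| Place | Use | CT/MRI | B-ultrasound | X-ray | Limit or safeguard |
|---|---|---|---|---|---|
| 3.1 | tumour imaging | yes | no | no | none needed |
| 8 | efficacy, from cycle 3 | yes | no | no | none needed |
| 7.1 row | baseline and on study | yes | yes | yes | note d only |
| 7.2 | baseline | yes | yes | yes | none |
| 7.3 item 3 | efficacy evaluation | yes | yes | no | none |
| 7.4 | efficacy, extension phase | yes | yes | no | none |
| Note d | chest, abdomen or pelvis negative at screening | to confirm a positive | yes | yes | positive confirmed by CT/MRI |

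Section 7.3 cannot be squared with 3.1, nor with Attachment 1 on ultrasound. Section 7.2 sits badly with entry criterion 2: the 10 mm it requires of a measurable lesion is Attachment 1's threshold for CT (or calipers), while the chest X-ray threshold is 20 mm. Section 7.4 matters less for the primary analysis, because subjects who enter the extension phase at progression have already had their PFS event.

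**2. What note d can and cannot cause**

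- *False negatives.* CT or MRI is triggered only by a positive X-ray or ultrasound. Confirming positives does nothing for a lesion the first test missed. Attachment 1 itself says CT is more sensitive than X-ray for new lesions.
- *False positives.* The confirmation step guards against these if the screening negative came from CT or MRI. If it came from X-ray or ultrasound, as 7.2 allows, the confirmatory CT is the first cross-sectional look. Attachment 1, section 4.3.5, says "A lesion identified on a follow-up study in an anatomical location that was not scanned at baseline is considered a new lesion". The protocol does not say whether a region seen only by X-ray or ultrasound counts as scanned. The same section requires a new lesion to be unequivocal and not the product of a changed modality, which limits this route.

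**3. The plan's own figures, for background**

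Inputs from 3.3 and 10.3: medians 5.8 and 12 months, 24 months' accrual plus 12 months' follow-up, 50 per arm, two-sided 0.05, 15% drop-out. Events are computed for exponential PFS with uniform accrual.

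- HR = 5.8/12 = 0.483.
- Event probability = 1 - (e^(-12λ) - e^(-36λ))/(24λ), with λ = ln 2/median. Treatment: 0.729 × 50 = 36.5. Control: 0.922 × 50 = 46.1. The plan states 37 and 46.
- Power at 83 events (Schoenfeld) = Φ(√83/2 × |ln 0.483| - 1.96) = 91.2%, or 90.8% at the final nominal level 0.0474. The plan states 90%.
- 50/0.85 = 58.8, so 59 per arm, as stated.

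These figures reproduce, and nothing in this point changes them.

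**4. Illustration of late detection**

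The protocol does not give the share of progressions that would be found late or the delay, so both are assumed. Simulation: 1,500 trials per scenario, 50 per arm, exponential PFS, visits at weeks 4 and 8 and then every 8 weeks, every event a progression, no drop-out, final boundary |Z| > 1.9825 with no interim look. One missed visit on the 8-week schedule is about 1.8 months (8/4.345). Where a cell has two values, they are for one and two visits late.

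| Scenario | Power (%) | HR | Control median (months) | Treatment median (months) |
|---|---|---|---|---|
| Visits as scheduled, none late (two runs) | 91.3 / 90.1 | 0.445 / 0.450 | 6.75 / 6.82 | 13.07 / 13.15 |
| 10% late, both arms | 90.0 / 89.9 | 0.454 / 0.450 | 7.02 / 7.19 | 13.20 / 13.48 |
| 30% late, both arms | 91.0 / 87.9 | 0.447 / 0.451 | 7.44 / 8.06 | 13.78 / 14.31 |
| 50% late, both arms | 88.9 / 88.9 | 0.453 / 0.456 | 7.79 / 8.89 | 13.96 / 15.07 |
| 30% late, treatment arm only | 93.5 / 96.5 | 0.422 / 0.391 | 6.85 / 6.78 | 13.66 / 14.26 |

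The HR is a one-step log-rank estimate. With exact event times it gives 0.464 for a true 0.483, so only the movement between rows should be read. The Monte Carlo error of the power is about √(0.9 × 0.1/1500) = 0.8 percentage points, so differences of one or two points are close to noise.

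**The case against.** The best defence is of note d, and much of it stands. The note covers only chest, abdomen or pelvis found negative at screening, so it does not by itself displace CT or MRI of known target lesions. Attachment 1's same-method rule applies to lesions already identified, and such a region has none. Its objection to ultrasound concerns measuring size, whereas note d uses ultrasound to look for disease. For new lesions seen on ultrasound, Attachment 1 advises the very CT or MRI confirmation that note d requires. Chest X-ray is less preferred there, not forbidden.

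The defence does not reach 7.2 and 7.3. Section 7.2 leaves the baseline modality open. Section 7.3 names ultrasound for efficacy evaluation itself, without note d's limit to negative regions or its confirmation step. Nor does it answer the false-negative problem.

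A reader might also infer that the treatment comparison is biased or under-powered. The documents do not support that. The trial is double-blind with one imaging schedule for both arms, and equal delay leaves the HR nearly unchanged. The one-arm row shows what a difference between arms would do, but nothing in the protocol implies such a difference.

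**Conclusion.** The protocol contradicts itself on how the primary endpoint is imaged, and 7.3 conflicts with the RECIST text it attaches. This should be fixed, but it does not undermine the design.

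The main risk is late detection of new lesions in regions followed under note d. False progression is a smaller risk, confined to subjects whose baseline was X-ray or ultrasound or whose efficacy was read by ultrasound under 7.3. Both are risks, and the documents do not show that progression will in fact be missed or wrongly called.

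The size cannot be derived from the protocol. Under the assumptions above (10-50% of progressions found one or two visits late, equally in both arms), the control median goes from about 6.8 to 7.0-8.9 months, the treatment median from about 13.1 to 13.2-15.1 months, and power stays at about 88-91%. The likely harm is to the absolute medians and their comparability with other RECIST 1.1 trials, more than to the test.

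Two stronger readings should be resisted. A share of the 83 events could be declared delayed (20-40% would be 17-33), but that share has no source, and it treats every PFS event as a progression and every one as delayed. Nor do 3.1 and 8 plainly require CT or MRI of every negative region at each visit, since neither names regions. Attachment 1, section 4.5, allows some non-target organs to be evaluated less often.

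**What to change.** - In the 7.1 imaging row, 7.2, 7.3 and 7.4, remove X-ray and B-ultrasound as RECIST efficacy modalities. State CT or MRI at baseline, and the same modality for each lesion at every assessment, in line with 3.1, 8 and Attachment 1.
- In note d, require that a region be called negative at screening only on CT or MRI. Keep X-ray or ultrasound as a trigger only, and keep the existing CT or MRI confirmation.
- Reconcile note d with 3.1 by saying how regions negative at screening are followed. This is a choice for the sponsor: routine CT or MRI of them would reduce late detection but adds scans and radiation at each visit.

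The cost is amendment wording plus some added CT or MRI at baseline, with its radiation, for subjects who would otherwise have had X-ray or ultrasound. No sample-size or event figure changes.

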# 7.2 Visit during the screening

The screening visit should be carried out within 14 days before the start of the trial. Informed consent should be signed, imaging examination (X-ray/CT/MRI/B ultrasound), ECG examination should be carried out. In case of precordial pain, palpitation and other symptoms, myocardial enzyme spectrum should be monitored (creatine kinase, lactate dehydrogenase, aspartate aminotransferase, creatine kinase isoenzyme,  $\alpha$ -hydroxybutyrate dehydrogenase) and color Doppler ultrasound should be performed (if necessary). Medical history should be collected within 7 days before the start of the trial, including previous treatment history, vital signs, physical examination and ECOG PS score, blood pressure test, blood routine (hemoglobin (HB), red blood cell (RBC), white blood cell (WBC), absolute neutrophil (ANC), neutrophil ratio (N), lymphocyte ratio (Lym), monocyte ratio (Mon), platelet count (PLT)), urine routine (urine protein, urine red blood cell (microscopic examination), urine white blood cell (microscopic examination)), stool routine, liver and kidney function (total bilirubin (TBIL), direct bilirubin (DBIL), indirect bilirubin (IBIL), ALT, AST, AKP, TP, ALB, BUN, Cr, UA, γ-GT, LDH), electrolytes (K, Na, Cl, CA), phosphorus (P)), coagulation function (PT, APTT (thrombin time), TT, fibrinogen (FBG), international standardized ratio (INR)), serum Tg and TgAb, thyroid function (FT3, FT4, TSH, RT3 [RT3 can be selected as needed]), life quality score, Hamilton Depression Scale score and (serum) pregnancy test (if there are clinical indications indicating pregnancy is possible) etc. Tumor samples (tissue and blood) are collected when subjects include in this study. If a tumor sample is not collected, the reason should be record.

